1. BACKGROUND AND SIGNIFICANCE

This project addresses an issue of substantial public health significance: enhancing the uptake of the growing list of patient-centered evidence-based addiction treatment e-health technologies.

Substance Use Disorders (SUDs) Impact on Society and Health. Every day on average, 96 Americans die due to opioid overdoses and another 6 die due to alcohol poisoning, making SUDs the third-leading cause of preventable death in the United States.⁸ Many injuries and

diseases (e.g., cancer, diabetes, cardiovascular problems, cirrhosis, and HIV/AIDS) are caused or exacerbated by alcohol abuse.⁹ Despite the health and societal consequences of SUDs, just 9.2% of those who need treatment receive it⁷ and, for those treated, 75% fail to achieve longterm sobriety.¹⁰ **The gap between the need for and the effectiveness of SUD treatment services calls for implementing fundamentally different treatment modalities to improve SUD.**

Patient-centered Mobile E-health: A Potential Answer? Patient-centered mobile e-health technologies offer innovative ways to improve treatment and recovery supports for SUDs.¹¹ Seventy-seven percent of the adult population in United States currently have a smartphone,¹² as do 74% of adults accessing Iowa SUD treatment clinics. By 2020, over 95% of the US population is expected to have smartphone access.¹² Meta-analyses of mobile behavioral ehealth interventions have found superior treatment outcomes when compared to treatment as usual.^{13,14} The combination of consumer interest, research evidence, and the number of research dollars being dedicated to evaluating these technologies will continue to place positive pressure on the use of e-health. **Despite the promise of e-health, its potential benefits are far from being realized.**¹⁵⁻¹⁷ A prominent example of this is in SUD care. Despite the availability of evidence-based e-health tools such as the Drinker's Check-up,^{18,19} Therapeutic Education System (TES),²⁰ CBT4CBT,²¹ and A-CHESS, none of these technologies are used by >1% of SUD treatment providers.²² **This proposal tests the premise that an evidence-based technology implementation framework can reduce the gap between patient-centered ehealth evidence and practice.**

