3. SELECTION OF SUBJECTS

This study will engage SUD organizations, counseling and peer recovery support specialist staff at those organizations, and patients of those organizations.

Organizations: Sixteen SUD organizations in Iowa, with a total of forty sites, have agreed to participate in the project.

Counselors: The site coordinator will invite all outpatient counselors serving adult patients employed by the 16 SUD organizations to be part of the study as part of their role in the participating organizations. Any counselor may formally decline to participate during the training or any time thereafter.

Peer Recovery Support Specialists: Peer Recovery Support Specialists associated with the organization will be invited to be part of the study. Any Peer Recovery Support Specialists may formally decline to participate during training or any time thereafter.

Patients: We will aim to enroll 1,800 outpatients from the 16 enrolled organizations. Each organization is expected to have about 516 A-CHESS-eligible patients on average. We estimate that we will recruit a conservative 30% (or approximately 43 per organizational site) for a total n=1,800 patients in the study. We will recruit patients for the 18-month intervention period plus 6 months into the maintenance period. Patients are eligible for the study if they:

- Are 18+ years old
- Understand English
- Have a SUD diagnosis
- Have access to a smartphone

All patients will be offered the opportunity to complete a survey through REDCap. To date, n=520 patients have created an A-CHESS account. We will also conduct in-depth interviews with 40 patients who have created an A-CHESS account.

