% who download A-CHESS app and frequency of A-CHESS use in days	Gustafson et al. ⁵⁰	A-CHESS Server - Monthly (Ms 11 - 47) IDPH – Monthly (Ms11 - 47)
Adoption		
% Counselor Using A-CHESS	Knight et al. ⁵⁹	Organizational Survey & A-CHESS Logs
Effectiveness		
Retention (Length of Stay)	Simpson et al. ⁶¹	IDPH- Ms 11 - 50
Maintenance		
Finance Resource Availability	Klein ⁶²	Organizational Survey – Ms 12, 30

Measurement	Measure Source	Data Source/Frequency (for Cohort 1)
A-CHESS Implementation Fidelity	Developed for this trial	Staff Survey – Ms 12, 30
Organizational Change Manager (OCM)	Gustafson et al. ⁶³	Staff Survey – Ms 11, 12, 30
Patient COVID-19 Survey		
Patient socio-demographic and descriptive characteristics: age, race/ethnicity, sex, gender, sexual orientation, education, marital status, income, housing, family size, employment status, health insurance	PhenX repository	Patient COVID-19 Survey – once during March 2021
Criminal justice history	Justice Community Opioid Involvement Network	
Alcohol Use Disorder Severity	Saunders et al.; Babor et al.	
Substance Use Disorder Severity	Skinner	
Loneliness	Hays & DiMatteo	
Anxiety	Cella et al.	
Substance use disorder recovery strengths	Vilsant et al.	
COVID-19 risk and protective behaviors and impact on daily living	Adapted from several COVID-19 surveys	

Qualitative Interviews: Qualitative data will be gathered from organizational staff at four points. Qualitative interviews with clinicians and peer recovery support staff will occur during the intervention phase. The goal of the interviews is to gain a better understanding of patterns with app adoption and use. Phone interviews of up to 30 minutes will be conducted with approximately 15 people at various sites. The interviews will be audiotaped (with participant permission), but the staff person's identity will be protected and in no way be linked to results.

Additionally, the study, interviews with staff from a randomly selected site in all organizations will occur at the end of intervention phase and again at the same site at the end of sustainability phase. The intent of the surveys is to gain a retrospective understanding of what occurred during implementation. Phone interviews of up to 30 minutes will be conducted with up to four people in at each site. The interviews will be audiotaped (with staff participant permission), but the staff person's identity will be protected and in no way be linked to results.

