Use data: A-CHESS use data will be collected monthly to assess the percentage of eligible patients who download the A-CHESS app per month per site and the frequency of use by app user. For the percentage who download A-CHESS, data will be collected during the 18-month intervention period and 6 months of post-intervention period for that organization. Frequency of use data for an individual user will be collected during the 12-month period following initial use of A-CHESS. The app automatically collects use data by placing "cookies" on patients' smartphones (with patients' consent) when they enroll in the study. Data are stored on a central server at CHESS. Electronic data, such as A-CHESS use data, will be stored on a secure DoIT server which is backed up according to a standard protocol. Access to this data will be limited by granting individuals access via their UW user log-in.

The Iowa Department of Public Health (IDPH) will also provide data available through existing IDPH administrative databases. A preliminary analysis of *organizational* data will compare baseline characteristics between the NIATx-TI and Product Training alone organizations, as well as organizations enrolled in the project and eligible organizations not participating (Admissions, Rural v. Urban, and Gender/Age/Ethnicity, and Poverty Level), using the National Survey of Substance Abuse Treatment Services (N-SSATS)⁵⁵ and Treatment Episode Data Set (TEDS)⁵⁶ data definitions.

During the study, IDPH will provide *patient* demographic data (gender, age, and ethnicity, using TEDS definitions) for all patients by organizational site. As part of the organizational survey, we will include questions about *counselors'* gender, ethnicity, and race.

Retention data will be collected by IDPH and provided monthly using existing data.

We will use UW Box to store data received from IDPH.

Supplemental COVID-19 Study – Patient Surveys and In-Depth Interviews

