We will create and distribute an information sheet for staff giving them the option to decline to participate in the trial or A-CHESS distribution.

Organizational Data: We will assess Financial Resource Availability Inventory, A-CHESS Implementation Fidelity, and List of Counselors (for counselor A-CHESS participation rates) at two points during the study - at organizational baseline (M 11 - 14) and end of the intervention period (M30 - 33) (M=months are in a range due to the 4 study periods) The Iowa Department of Public Health (IDPH) will provide, by site, aggregate data on Admissions, and Rural v. Urban. This data will be collected from IDPH databases at months 11, 22, 34, and 42

Consumer level: Eligible consumers will be identified in real time during their first three outpatient appointments with a participating SUD treatment site. Site counselors will provide information about the study. If the patient is interested in the study, the counselor will provide a brief introduction to A-CHESS and provide information to the client with the URL to download A-CHESS. If the patient chooses to participate, informed consent will be documented via an IRB-approved consent form on the A-CHESS app.

To be eligible for A-CHESS, SUD consumers must: 1) be >18 years old; 2) understand and agree to an English language consent form via the A-CHESS app; 3) have access to a mobile smartphone, and 4) have an SUD diagnosis.

We anticipate enrolling consumers to use A-CHESS (approximately 43 per organizational per site, for a n=1,800 for the study). The state (IDPH) will provide de-identified data including gender, age, ethnicity, poverty level, and units of service for each site.

During approximately March 2021, all patients who have signed up for an A-CHESS account (to-date n=520) will be invited to participate in a one-time, online, self-report survey through REDCap.

Sources of Materials

All data will be coded before reaching evaluation staff. These include data collected by A-CHESS App server on A-CHESS use as well as organization and staff interview and qualitative survey data. Coding of consumer and counselor/staff data will take place, where necessary, by replacing identifying information (such as consumer and staff names) with code numbers prior to data analysis. A unique study ID number will be assigned to all patient surveys and in-depth interviews. Names collected through the informed consent process will be stored separately.

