Site-level aggregate data will be received from the Iowa Department of Public Health (IDPH). The individual de-identified consumer data from the state database will be transmitted to the University of Wisconsin database administrator ([name]). The evaluation team will monitor overall use and effectiveness of A-CHESS through consumer data directly from the A-CHESS App server.

Consumer level:

A-CHESS usage based on A-CHESS App server tracking of consumer use of their smartphones (for initial log-in, duration and frequency of use).

Surveys and in-depth interviews about COVID-19 associated anxiety and loneliness.

Staff level:

The OCM Survey will collect data on the organizational philosophy. The A-CHESS Implementation Fidelity will document the fidelity to the NIATx TI implementation process.

Counselor level:

The organizational survey will be used to document all active counselors per site. The following information will be gathered about each counselor: title or certification, age, gender, ethnicity, and race. The Iowa Consortium for Substance Abuse Research and Evaluation will check for any changes in counselor employment during quarterly check-ins. This will be used to create and maintain a counselor list to be compared to the counselors listed during A-CHESS log-ins to develop the % of Counselors Using A-CHESS Measure. This same data will not be collected for the Peer Recovery Support Specialist.

Organization level:

IDPH database will provide program characteristics and organizational descriptive characteristics and will collect data on the nature and scope of the individual SUD treatment sites. Site-level aggregate data on adults with SUD diagnosis by organization by site, including gender, age, and ethnicity. Retention data will also be obtained from IDPH.

The organizational survey will also collect the names and demographics of all counselors and Finance Resource Availability assessment. The Finance Resource Availability assessment assesses the resources the organization dedicates to adoption of the targeted technology.

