7. MEASUREMENT OF EFFECT

All scales used in this study have good psychometric properties with similar populations. Listed below are the factors to be measured and measurement instruments with references to validation studies.

Descriptive Statistics - Organizational traits such as admission and rural v. urban will be obtained via IDPH data at four points during the study (N-SSATS⁵⁵). Patient traits such as age, gender, ethnicity, and poverty level will also be obtained at four points during the study via IDPH data (TEDS⁵⁶). Counselor traits such as gender, ethnicity, race, and certification or education level will be obtained via the organizational survey.

REACH - The percentage of patients that download the A-CHESS app and frequency of use in days will be obtained monthly during the study via the A-CHESS server and IDPH data.⁵⁰

Adoption - The percentage of counselors using A-CHESS will be assessed via the organizational survey and A-CHESS logs.⁵⁹

Effectiveness - Retention (length of stay) will be assessed using IDPH data.⁶¹

Maintenance - The organizational survey, which will be administered at two points during the study, will assess Financial Resource Availability.⁶² The staff survey will assess A-CHESS Implementation Fidelity (developed for trial) and Organizational Change Manager (OCM)⁶³. The OCM and A-CHESS Implementation Fidelity will be administered at two points during the study.

Patient COVID-19 Surveys – Surveys will assess how A-CHESS use may have lessened the impact of COVID-19 on anxiety and loneliness. We will collect several patient socio-

demographic traits as recommended by NIH, including age, race, self-identified gender, sex at birth, approximate income level, educational attainment, sexual orientation, marital status, housing type, family size, health insurance. We will use several validated measures to assess patients' substance use severity, loneliness, anxiety, and substance use disorder recovery strengths. Where validated measures are not available due to the rapidly emerging COVID-19 situation, we have drawn measures from existing population-based studies recommended by the National Institutes of Health.

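### The primary Reach percentage is defined over eligible patients, but its named data sources cannot apply the smartphone or English criteria, so absolute Reach would be understated by roughly 5% to 26%

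*Combined protocol and SAP*

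**What the plan says.** Section 5 (Use data) describes the primary Reach measure as "the percentage of eligible patients who download the A-CHESS app per month per site". Section 9 likewise models a percentage based on eligibility, by site and month. Section 7 words the same measure as a percentage of patients, without the word *eligible*.

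Section 3 sets four eligibility criteria: adult age, an SUD diagnosis, understanding English, and "Have access to a smartphone". Section 5 (Consumer level) repeats them.

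On sources, Section 7 says the percentage and the frequency of use "will be obtained monthly during the study via the A-CHESS server and IDPH data". Table 1 names the same two sources for Reach, both monthly.

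On what IDPH supplies, Section 5 lists "Site-level aggregate data on adults with SUD diagnosis by organization by site, including gender, age, and ethnicity" (Sources of Materials, Organization level). Under Consumer level it says: "The state (IDPH) will provide de-identified data including gender, age, ethnicity, poverty level, and units of service for each site". Admissions, rural or urban status and retention also come from IDPH.

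On smartphone access, Section 1 gives 77% for US adults, "as do 74% of adults accessing Iowa SUD treatment clinics", and then projects over 95% of the US population by 2020.

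**The concern.** Two of the four eligibility criteria cannot be applied with the data that the plan names for the denominator. Staff at the sites identify eligible patients as they present, but the plan describes no screening or eligibility log that would give a count. Followed as written, the plan produces downloads divided by adults with an SUD diagnosis and reports the result as a share of eligible patients.

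Reach is the primary outcome, and under RE-AIM its absolute level is itself a result. If the denominator includes people who could not have enrolled, the reported level is too low, and so is a difference between arms expressed in percentage points. Section 8 matches on the number of rural sites because of the digital divide. The plan therefore expects access to vary between sites, and the size of the error would vary with it.

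**Working it through.** **1. Which source supplies the denominator.** Two sources are named. The server records people who have signed on, so it supplies the numerator. That leaves IDPH for the denominator. This is an inference by elimination; no sentence states it.

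**2. Which criteria that source can apply.**

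| Criterion (Section 3) | In the IDPH items listed in Section 5? |
|---|---|
| Adult | Yes |
| SUD diagnosis | Yes |
| Understands English | Not listed |
| Smartphone access | Not listed |

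The count of eligible patients is also unsettled elsewhere. Section 3 gives 516 per organization: 516 × 16 / 40 = 206 per site, of which 30% is 62. Section 9 uses 62 as the number of *eligible* patients per site, while Section 3 gives about 43 per site as the 30%.

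**3. Size of the understatement.** Let s be the share of IDPH-counted adults with smartphone access. Then reported Reach = true Reach × s. If s is equal in both arms, the reported difference = true difference × s. Inputs: s = 0.74 and 0.95 (Section 1), Reach 30% (Section 3), difference 12.4 points (pilot, Section 9).

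| s | 30% Reach reads as | 12.4 points reads as | Understated by |
|---|---|---|---|
| 0.95 | 28.5% | 11.8 | 5% |
| 0.74 | 22.2% | 9.2 | 26% |

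The 12.4-point column applies only if the pilot effect was measured among technology-eligible clients. The documents give no figure for patients excluded by language.

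**4. Relative effect.** With equal s, the ratio of arms is unchanged. At an assumed 12.4% v 24.8% (a doubling), s = 0.74 moves the odds ratio only from 2.33 to 2.22.

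**5. Power.** First, the plan's own figure: design effect 1 + 61 × 0.10 = 7.1; effective n per arm 20 × 62 / 7.1 = 174.6; power = Φ(0.352 × √(174.6/2) − 1.96) = 0.908. The stated .90 is reproduced (two-sided test assumed).

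Next, with proportions: power = Φ{[Δ − 1.96√(2p̄(1−p̄)/n)] / √[(p₁(1−p₁)+p₂(1−p₂))/n]}.

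- True denominator, assumed 12.4% v 24.8%, n = 174.6: power 0.849. This is below 0.908 because the implied effect is 0.124/√(0.186 × 0.814) = 0.319, not 0.352. Only the change from 0.849 matters here.
- s = 0.74: the arms read 9.2% v 18.4% and the cluster size becomes 62/0.74 = 83.8. The between-site SD shrinks by the same factor, so the ICC becomes 0.74² × 0.01514 / (0.1376 × 0.8624) = 0.070. The design effect is 1 + 82.8 × 0.070 = 6.78, n = 20 × 83.8 / 6.78 = 247, and power is 0.844.
- s = 0.74 with the ICC held at 0.10: power 0.718.

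With assumed control Reach of 20% or 30% and the ICC rescaled, power moves from 0.752 to 0.745 and from 0.675 to 0.664.

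**6. Unequal access (illustration, assumed values).** With true Reach of 30% v 42.4%, access of 0.70 (control) and 0.78 (NIATx-TI) gives 0.424 × 0.78 − 0.30 × 0.70 = 12.1 points. Reversed, it gives 0.424 × 0.70 − 0.30 × 0.78 = 6.3 points. The error can go either way relative to the 9.2 points under equal access.

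**The case against.** The strongest reply is that the documents leave the denominator undefined; they do not define it wrongly. The sentence on adults with an SUD diagnosis lists data received and does not mention Reach. Both IDPH lists use the word *including*, so they may not be exhaustive. This stands as far as it goes: the denominator is an inference. But no other source is named, and a primary measure should not depend on an unlisted field.

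A reader might infer that Reach is understated by a quarter. That uses only the 74% figure. The next sentence in Section 1 projects over 95% nationally by 2020, and accounts were still accruing around March 2021. The national figure need not hold for Iowa SUD patients, so the share during the trial is unknown. A range is what the documents support.

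A reader might also infer that power falls from about 0.91 to between 0.68 and 0.77. Those figures come from scaling d to 0.352 × 0.74 = 0.260, or to 0.287 with the binomial SD rescaled at 30% Reach, while keeping the ICC at 0.10 and the cluster size at 62. A common multiplier on every site also shrinks the between-site SD, and the wider denominator makes clusters larger. With both allowed for, the loss is about one point or less. The pilot's denominator is not given either; if it was all clients, the planned effect is already on the wider scale.

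Two further points stand. Section 8 already matches on rural sites, which limits imbalance but does not remove it with 16 organizations. And multiplying every denominator by one constant says nothing about the comparison between arms; it informs only the absolute level.

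**Conclusion.** The point holds as a mislabelled and undefined primary denominator. With the sources named, the plan cannot compute a percentage of eligible patients; it can compute a percentage of adults with an SUD diagnosis. Absolute Reach and the absolute arm difference would be understated by roughly 5% to 26% before any language exclusion. This assumes that IDPH supplies the denominator, that access lies between the two figures in Section 1, and, for the difference, that access is equal by arm and the planned effect refers to technology-eligible clients.

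The documents do not support a claim that the relative effect is biased under equal access, or that the stated power is materially lost. The latter rests on between-site variation scaling with the mean. Days of use, the other Reach measure, does not use this denominator. The randomized comparison remains valid; what changes is what the trial can say about the level of Reach.

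**What to change.** 1. In Sections 2, 5 and 9, define the primary denominator as the monthly site count of adult SUD patients that IDPH supplies, and stop calling it eligible. Table 1 already lists a monthly IDPH feed for Reach, whereas Section 5 describes site admissions at only four time points. The definition should name the feed used and say whether the count is limited to outpatients.
2. Report a labelled sensitivity estimate of Reach among eligible patients, with the denominator multiplied by 0.74 and by 0.95. State that it concerns the absolute level only and leaves language exclusions out.
3. Include rural status as a covariate in the Section 9 mixed model. It is already a matching trait, and smartphone access is expected to differ by it.

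The cost is a slightly lower reported percentage, one sensitivity analysis and one model degree of freedom. The power statement need not be restated on this account.
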